and how their communication is with the practitioner (19,20). Adherence to inhaled medications is lower than to oral tablets or injectable medications. The more complex and the more times the patient has to remember to take the medication, the harder it is to establish optimal adherence (19,20).

CRSwNP a chronic disease like asthma, where low adherence is often seen in mild to moderate cases compared to severe cases of CRSwNP (21). However, the clinical perception is that not all patients take all their daily doses, but few scientific studies have focused on this. The difficulty in treating CRS is that the patient must apply nasal steroid 1-2 times daily as well as it must be combined with nasal saline irrigation at least once daily. Decreased adherence is led by poor disease control. It is therefore important to support and strengthen patient adherence to CRS and asthma in order to achieve good disease control (21).

Population and recruitment

The study population consists of patients referred to the Respiratory Clinic in the Department of Ear, Nose and Throat Surgery and Audiology, Rigshospitalet. Patients are recruited by initial visits to the Respiratory Clinic, where they receive oral and written information about the project. If patients wish to participate, they must complete a written consent form for participation in the project. In order to be included in the study, the following inclusion and exclusion criteria must be met:

Inclusion criteria	Exclusion criteria
Adherence to MARS- 5 L/N ≤35	Adherence to MARS-5- L/N >35
at first visit	points at first visit
Diagnosed with asthma (with and	Do not have smartphone
without allergic rhinitis) at initial	
visit	
Able to use smartphone	Does not read or speak English
Able to use smartphone	Does not read of speak Elignish
ACQ \geq 1.2 or ACT \leq 15 (partially	Other illness requiring regular
uncontrolled asthma)	medication
Be over 18 years of age	Pregnancy and pregnancy that
	started during the study time pe-
	riod
SNOT-22 score ≥35	Servere psychological comorbidi-
	ties
Diagnosed with CRSwNP	

Material and method

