The study is a randomized trial with a control group and an intervention group. Patients will be randomized via Research Electronic Data Capture (Redcap), a secure web application for building and managing databases and online questionnaires. The system was developed at Vanderbilt University, which released the first version in 2008 (22). Patients will be randomized to the control or intervention group. Randomization will be stratified by gender. Patients in the intervention group will receive systematic and structured nursing guidance regarding their adherence, which includes proper use of nasal irrigation once or twice daily, nasal steroid/drops, use of inhaled medications, follow-up of smoking status. The intervention group will receive guidance videos which have been prepared prior to the study and will be standard for the intervention group. Guidance videos will cover the correct use of nasal irrigation, inhalation steroid, and nasal steroid/drops. The control group and intervention group will receive twice a week text message reminders to take their medications and to rinse their nose.

Their adherence will be measured via MARS-5-N and MARS-5-L f. Total MARS-5-N/L will be measured at their initial visit and four months after teaching or usual care. The same form will be given at both visits. Patients in the control group will not receive systematic and structured nursing care regarding their adherence, but their adherence will be measured via MARS-5-N and MARS-5-L max score is 50 when measuring a adherence in global airways. In a pilot study, mean (SD) 20.4 (6.28) is found for MARS-5-L, and for MARS-5-N mean 20.7 (5.57) is found. 41 points correspond to 80% of total of both MARS-5-L and MARS-5-N. A satisfactory adherence should be 80%. In another pilot study, patients were measured twice with at least one month in between. Here, the mean of the inter-individual difference at MARS-5-L/N first and second time is equal to 5.34(2.62). These two pilot studies will be used for the final power calculation.

Statistics data analysis and power calculation

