The statistical analysis of data is performed using IBM SPSS Statistics. Results will be presented as mean, SD, range and 95% CI. The parametric data will be compared using paired and unpaired tests, and non-parametric data using Wilcoxon Signed-Ranks Test and Mann-Whitney Test, respectively. Categorical variables are tested by chi-square test. A P-value <0.025 is considered significant for a pooled MARS-5-N and MARS-5-L For a pooled MARS5-L/N questionnaire, the total score would be 25x2= a total of 50 points theoretically. A safe difference is calculated from the intraindividual difference detected in the pilot study (mean 5.34 (2.62)), but based on the pilot study an SD and mean are calculated on the difference between MARS-5-L/N, which corresponds to an SD 5.34 and mean 2.62. With a MIREDIF of 5 and the largest SD of 6.28 by single measurement with a p-value of 0.025% (0.05/2) because there are two schedules and a power 80%, this would require 36 patients in each group including a dropout of 20%.

In addition, ensuring that MARS-5-N/L are both above 80% (the standard requirements for good adherence); and hoping for 100% adherence in the intervention group, versus 80% in the control group, this would require 39 in each group. - And including the 20% dropout rate, the total population would be 47 in each group.

Project participants

[name], nurse, Department of Otolaryngology and Audiology

[name], clinical nurse specialist and ph. Student, Department of Ear, Nose and Throat Surgery and Audiology

[name], Senior Physician, Department of Ear, Nose and Throat Surgery and Audiology

[name], Professor, MD, Department of Ear, Nose and Throat Surgery and Audiology

Risks and side effects

There are no serious side effects associated with participation in the trial. There may be a risk that patients in the control group of the study may have a worse prognosis/prognosis than patients achieving good adherence (80%) in the intervention group. To reduce this risk, patients in the control group are offered the same guidance as those in the intervention group at the end of the trial.

Information from patient records

No personal data will be collected from patient records. Data included in the study are from patient questionnaires and from results of clinical objective tests.

Processing of personal data

The project is carried out in compliance with the Data Protection Regulation and the Data Protection Act.

Economy

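### The 20% dropout allowance is added by multiplying by 1.2, so the stated group sizes of 36 and 47 cover about 17% loss, not 20%; the effect on power is small

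*Combined protocol and SAP*

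**What the plan says.** Both sample sizes are in the combined protocol and SAP, under Statistics data analysis and power calculation.

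- **First size.** It is introduced by "With a MIREDIF of 5 and the largest SD of 6.28 by single measurement", with a significance level of 0.05/2 and 80% power. The result is that "this would require 36 patients in each group including a dropout of 20" per cent. The number before dropout is not printed.
- **Second size.** The text continues: "hoping for 100% adherence in the intervention group, versus 80% in the control group, this would require 39 in each group". It then adds that "including the 20% dropout rate, the total population would be 47 in each group". Here both ends of the dropout step are printed, but the test, alpha and power behind 39 are not.

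No inflation formula is given for either size, and the section does not say which of the two is the recruitment target. For the analysis of categorical data it says: "Categorical variables are tested by chi-square test".

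**The concern.** A dropout rate is normally the share of enrolled patients who are lost. To finish with n completers after losing 20%, one must enrol n/(1 − 0.20), which is n × 1.25. Multiplying by 1.2 adds 20% of the completers rather than allowing for the loss of 20% of those enrolled, and it always falls short.

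Both sizes are described as including 20% dropout. If they do not, a trial that loses exactly the planned share ends with fewer patients than its own calculation says it needs. At stake are the accuracy of the two statements and a small amount of power.

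**Working it through.** **Inputs.** From the power section: difference 5, SD 6.28, significance level 0.05/2 = 0.025 (the printed per cent sign after 0.025 is read as a slip), power 80%, rates 100% and 80%, sizes 36, 39 and 47, dropout 20%. Assumed: a two-sided test, because that reproduces the figures, and the same alpha and power for the second calculation, where they are not restated.

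**Normal quantiles.** z = 2.2414 (two-sided 0.025) and 0.8416 (80% power). Their sum is 3.0830, and its square is 9.505.

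**Reproducing 36.**
- n = 2 × (6.28/5)² × 9.505 = 29.99, so 30 per group.
- 30 × 1.2 = 36, the printed figure.
- 30/0.8 = 37.5, so 38.

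The 30 is therefore inferred. A noncentral t calculation gives 32 instead, and 32 × 1.2 = 38.4, which does not lead to 36.

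**Reproducing 39 and 47.**
- Two proportions, unpooled variance: n = 9.505 × (1.00 × 0 + 0.80 × 0.20)/(0.20)² = 38.02, so 39 per group.
- 39 × 1.2 = 46.8, so 47, the printed figure.
- 39/0.8 = 48.75, so 49.

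The pooled-variance version gives 42 and does not reproduce 39. Fisher's exact test at 0.05 also first passes 80% power at 39 (0.7996 at 38, 0.820 at 39). The method behind 39 is thus not settled by the text, but the step from 39 to 47 is printed and does not depend on it.

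**Loss that each size absorbs.**

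| Enrolled per group | Needed | Left after 20% loss | Loss absorbed | n/(1 − 0.20) |
|---|---|---|---|---|
| 36 | 30 (inferred) | 28.8 | 1 − 30/36 = 16.7% | 38 |
| 47 | 39 (printed) | 37.6 | 1 − 39/47 = 17.0% | 49 |

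**Power after a 20% loss.**
- 36 enrolled, means formula at 28.8: 5/(6.28 × √(2/28.8)) = 3.021; 3.021 − 2.241 = 0.780; power 0.782, against 0.800 at 30.
- 47 enrolled, unpooled proportions at 37.6: √(37.6 × 0.04/0.16) = 3.066; 3.066 − 2.241 = 0.825; power 0.795, against 0.811 at 39.
- 47 enrolled, Fisher's exact test at 0.05: 0.778 with 37 completers and 0.7996 with 38.
- 47 enrolled, exact power of the Pearson chi-square test without continuity correction at 0.025, 100% v 80%: 0.888 with 37 completers and 0.901 with 38. It first passes 80% at 33 per group.
- 47 enrolled, the 5-point comparison with SD 6.28: 0.882 at 37 and 0.887 at 37.6.

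**The case against.** The strongest reply is that nothing of substance depends on this. The gap is two patients per group and roughly 0.5 to 2 percentage points below 80% power. The passage reads most naturally as ending on 47, and in that case the 36 is not the target. After a 20% loss from 47, the 5-point comparison of the MARS-5 score, which is the primary measure, still has about 88–89% power on the plan's inputs. For 100% v 80%, the unrounded requirement is 38.02, so 37.6 is short by about 0.4 of a patient. The test named for categorical data is the chi-square, and its exact power at 0.025 with 37–38 completers is 89–90%.

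All of this stands, and it limits the weight of the point. It does not rescue the wording: 37.6 is still fewer than the 39 that the plan says it requires. One could also read 20% as a surplus added to the required number, but the plan calls it a dropout rate, and under that reading the text would still need rewording.

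Two stronger readings are tempting. A reader might infer that the trial is underpowered; the dropout step does not show that, for the reasons just given. A reader might also infer that the 100% and 80% rates behind 39 are wrong. The documents do not show that either: the 100% is openly presented as a hope, and the lower adherence figures that the Adherence section cites (50% for long-term treatment, 22%–78% in asthma and COPD) come from other settings. If the control rate were below 80% with 100% in the intervention group, power would rise, not fall.

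**Conclusion.** The point holds as a minor arithmetic error. Both sizes described as including 20% dropout cover about 17%. For 47 this follows from printed figures alone. For 36 it rests on the inferred 30, which in turn assumes a two-sided 0.025 and the normal approximation.

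The power figures carry more assumptions than the dropout arithmetic. The 79.5% for 47 depends on an inferred method, alpha and power behind 39. The 78% for 36 uses an SD of 6.28, which Material and method reports for MARS-5-L alone; using it here reproduces the plan's calculation and does not endorse it for the pooled score. On no reading examined here does the dropout step alone take power more than about two to three percentage points below 80%.

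**What to change.** Either of two edits would do.

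1. Keep 36 and 47, and state that they cover about 17% loss. Add that a 20% loss would leave about 29 and 38 completers per group, with power of about 78% and 79.5% on the formulas used. This costs only wording.
2. Use n/(1 − 0.20), giving 38 and 49 per group. This costs two more patients per group: 76 in total instead of 72, or 98 instead of 94.

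In the same edit, name the adopted size, print the pre-dropout number behind 36, and give the method, alpha and power behind 39. The last item matters for option 1, because the power to be restated for 47 depends on the method: about 79.5% on the unpooled formula, 89–90% on the exact chi-square at 0.025.
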